#### **4.2. Scientific Rationale for Study Design**

This study is a Phase 1, non-randomized, open-label study of PF-07321332 in participants with moderate hepatic impairment and participants with normal hepatic function, matched for age, body weight and, to the extent possible, for gender composition. Details on age and body weight matching criteria are specified in [Section 5.1](#).

PF-07321332 alone is primarily eliminated through a CYP450 mediated oxidation with CYP3A4 as the major contributor ( $f_m = 0.99$ ). However, in the presence of the CYP3A4 inhibitor ritonavir, preliminary data suggests renal excretion may play a significant role in PF-07321332 excretion. In FIH study, approximately 64.6% to 32.5% of the administered dose was excreted unchanged in urine and remaining drug may get eliminated via metabolism. Preliminary PBPK modeling suggests  $< 2 \times$  increase in AUC in mild hepatic impaired participants (Child-Pugh A) and  $< 3 \times$  increase in moderate (Child-Pugh B) hepatic impaired participants. Therefore, the PK will only be evaluated in moderately hepatic impaired participants. Ritonavir has not been studied in severe hepatic impaired patients and currently prohibited to be used in those population. Therefore, this study does not plan to evaluate PK in severely hepatically impaired participants.

A single dose of PF-07321332 was selected and is considered appropriate as available data do not indicate PF-07321332 PK are time-dependent, and hence, single dose data are considered predictive of steady state. As ritonavir is not eliminated renally, multiple doses of 100 mg ritonavir will be administered at -12, 0, 12, and 24 hours relative to PF-07321332 dosing to ensure adequate PK boosting effect over the duration of PF-07321332 exposure.

PF-07321332 is not extensively bound to human plasma proteins, with  $f_u$  of 0.31 observed in the in vitro protein binding study. Thus, no additional blood samples will be collected in this study for ex vivo protein binding analysis.

#### **4.2.1. Choice of Contraception/Barrier Requirements**

Human reproductive safety data are limited for PF-07321332, but there is no suspicion of human teratogenicity based on the intended pharmacology of the compound. Therefore, the use of a highly effective method of contraception is required (see [Appendix 4](#)).

CCI  
[REDACTED]  
[REDACTED]

#### **4.3. Justification for Dose**

A single oral dose of 100 mg PF-07321332, pharmacokinetically enhanced with ritonavir (100 mg at -12, 0, 12, and 24 hours relative to PF-07321332), is planned in this study. This is anticipated to be at the lower end of the clinically effective dose range, and below the anticipated Phase 2/3 dose of PF-07321332/ritonavir of 300/100 mg. Although single doses up to 750 mg PF-07321332 with ritonavir have been evaluated, exposure increased less than dose proportional within the 250 mg to 750 mg dose range evaluated. Therefore, 100 mg PF-07321332 is appropriate considering systemic exposures of PF-07321332 may be increased when administered in hepatic impairment.

When co-administered with ritonavir, doses of PF-07321332 up to 750 mg single dose and 500 mg q12h for 10 days were generally safe and well tolerated based on preliminary data from the Phase 1 Study C4671001. There have been no deaths or serious adverse events or SUSARs reported. Based on review of preliminary (unaudited) data, all reported adverse events have been of mild intensity. There were no clinically meaningful findings in vital signs, ECG, or potential Hy's Law cases reported during the study.

Using preliminary PBPK model, the projected AUC and  $C_{max}$  at the proposed dose are CCI [REDACTED] which are below the highest observed exposures at safe and tolerate dose in study C4671001 and are approximately 19  $\times$  and 25  $\times$  below NOAEL exposures observed in toxicity studies in rats, respectively.

The dose of ritonavir to be used in this study is 100 mg administered BID. This dose is the typical dose of ritonavir when dosed as PK enhancer.

#### **4.4. End of Study Definition**

The end of the study is defined as the date of the last visit of the last participant in the study.

A participant is considered to have completed the study if he/she has completed all phases of the study, including the last visit.

### **5. STUDY POPULATION**

This study can fulfill its objectives only if appropriate participants are enrolled. The following eligibility criteria are designed to select participants for whom participation in the study is considered appropriate. All relevant medical and nonmedical conditions should be

taken into consideration when deciding whether a particular participant is suitable for this protocol.

Prospective approval of protocol deviations to recruitment and enrollment criteria, also known as protocol waivers or exemptions, is not permitted.

### **5.1. Inclusion Criteria**

Participants are eligible to be included in the study only if all of the following criteria apply:

#### **Age and Sex:**

1. Participants must be 18 to 75 years of age, inclusive, at the time of signing the ICD.
  - **[For Cohort 1 only]** Each participant's age is within  $\pm 10$  years of the mean age of the hepatic impairment group. Attempts will be made to ensure that the male-to-female distribution in Cohort 1 is comparable to that in hepatic impairment cohort, Cohort 2.
  - Refer to [Appendix 4](#) for reproductive criteria for male ([Section 10.4.1](#)) and female ([Section 10.4.2](#)) participants.

#### **Type of Participant and Disease Characteristics:**

2. Participants who are willing and able to comply with all scheduled visits, treatment plan, laboratory tests, lifestyle considerations, and other study procedures.
3. **[For Cohort 1 only]** Male and female participants who are classically healthy having no clinically relevant abnormalities as determined by medical evaluation including medical history, physical examination including blood pressure and pulse rate measurement, 12-lead ECG, and laboratory tests. No known or suspected hepatic impairment.
4. **[for Cohort 2 only]** Stable hepatic impairment that meets the criteria for Class B of the CPC (refer to [Appendix 9](#)) with no clinically significant change in disease status within the 28 days prior to the Screening visit, as documented by the participant's recent medical history (for example: no worsening clinical signs of hepatic impairment, no worsening of total bilirubin or PT by more than 50%).

#### **Weight:**

5. BMI of 17.5 to 40 kg/m^2; and a total body weight >50 kg (110 lb).
  - **[For Cohort 1 only]** Each participant's body weight within  $\pm 15$  kg of the mean body weight of hepatic impairment group.

### **Informed Consent:**

6. Capable of giving signed informed consent as described in [Appendix 1](#), which includes compliance with the requirements and restrictions listed in the ICD and in this protocol.

### **5.2. Exclusion Criteria**

Participants are excluded from the study if any of the following criteria apply:

#### **Medical Conditions:**

1. Evidence or history of clinically significant hematological, renal, endocrine, pulmonary, gastrointestinal, cardiovascular, hepatic, psychiatric, neurological, or allergic disease (including drug allergies, but excluding untreated, asymptomatic, seasonal allergies at the time of dosing).
2. Any condition possibly affecting drug absorption (eg, prior bariatric surgery, gastrectomy, ileal resection).

**NOTE:** Participants who have undergone cholecystectomy and/or appendectomy are eligible for this study so long as the surgery occurred more than 6 months prior to Screening.

3. At screening, participants with a positive result for HIV antibodies.
4. **[For Cohort 1 only]** Participants with chronic liver disease including history of hepatitis, hepatitis B, or hepatitis C or evidence of active disease, at screening.  
**NOTE:** Participants with a previously positive hepatitis B surface antibody result due to vaccination are deemed eligible.

5. **[For Cohort 2 only]**
  - Hepatic carcinoma **or** hepatorenal syndrome **or** limited predicted life expectancy (defined as less than 1 year).
  - A diagnosis of hepatic dysfunction secondary to any acute ongoing hepatocellular process that is documented by medical history, physical examination, liver biopsy, hepatic ultrasound, computerized tomography scan, or MRI.
  - Signs of clinically active Grade 3 or Grade 4 hepatic encephalopathy (ie, > Grade 2 Portal Systemic Encephalopathy score; refer to [Appendix 9](#)).
  - Severe ascites and/or pleural effusion.
  - History of kidney, liver, or heart transplantation.

6. Other medical or psychiatric condition including recent (within the past year) or active suicidal ideation/behavior or laboratory abnormality or other conditions or situations related to COVID-19 pandemic (eg, Contact with positive case, residence, or travel to an area with high incidence) that may increase the risk of study participation or, in the investigator's judgment, make the participant inappropriate for the study.

**Prior/Concomitant Therapy:**

7. Participants who have been vaccinated with COVID-19 vaccines within the past 1 week of dosing.
8. Previous administration with an investigational drug within 30 days (or as determined by the local requirement) or 5 half-lives preceding the first dose of investigational product used in this study (whichever is longer).
9. Use of prescription or nonprescription drugs and dietary and herbal supplements within 7 days or 5 half-lives (whichever is longer) prior to the first dose of study intervention (Refer to [Section 6.8](#) Concomitant Therapy for additional details). Limited use of nonprescription medications that are not believed to affect participant safety or the overall results of the study may be permitted on a case-by-case basis following approval by the sponsor.

For participants with hepatic impairment, stable concomitant medications (including herbal supplements) may be given following **approval by the sponsor** if they are considered necessary for the welfare of the study participants (eg, standard therapy for underlying diseases), are not contraindicated with the IP, and are unlikely to interfere with the PK of the IP.

10. Current use of any prohibited concomitant medication(s) or those unwilling/unable to use a permitted concomitant medication(s) (Refer to [Section 6.8](#) Concomitant Therapy for additional details).

**Prior/Concurrent Clinical Study Experience:**

11. Previous administration with an investigational drug within 30 days (or as determined by the local requirement) or 5 half-lives preceding the first dose of study intervention used in this study (whichever is longer).
12. Participants with known prior participation (ie, randomized and received at least 1 dose of investigational product) in a study involving PF-07321332.

**Diagnostic Assessments:**

13. A positive urine drug test at Screening or on Day -1.

**NOTE:** Participants in Cohort 2 who have been medically prescribed opiates/opioids or benzodiazepines and report the use of these drugs to the investigator at Screening may be allowed to participate if approved by the sponsor.

14. In females of childbearing potential, a positive urine pregnancy test at Screening or Day -1.

15. Vital sign measurements at Screening that demonstrates:

**[For Cohort 1 only]** Screening seated BP  $\geq 140$  mm Hg (systolic) or  $\geq 90$  mm Hg (diastolic), following at least 5 minutes of rest.

**[For Cohort 2 only]**

- Screening seated BP  $\geq 180$  mm Hg and/or  $\geq 100$  mm Hg (diastolic) following at least 5 minutes of rest.

**NOTE:** If SBP is  $\geq 140$  mm Hg (for Cohort 1) **or**  $\geq 180$  mm Hg (for Cohort 2) or if DBP  $\geq 90$  mm Hg (for Cohort 1) or  $\geq 100$  mm Hg (for Cohort 2), the BP should be repeated 2 more times and the average of the 3 BP values should be used to determine the participant's eligibility.

- For participants with SBP  $\geq 160$  (and  $<180$ ) mm Hg **or** DBP  $\geq 95$  (and  $<100$ ) mm Hg, the period between Screening and Day -1 must be used to refine the doses of the agents used for management of BP with the aim to have stable BP by Day -1. Participants must have measurement on Day 1 of SBP  $\leq 160$  mm Hg **and** DBP  $<95$  mm Hg.

16. Screening standard 12-lead ECG that demonstrates:

- Clinically relevant abnormalities requiring treatment (eg, acute myocardial infarction, serious tachy- or brady-arrhythmias) or indicating serious underlying heart disease (eg, prolonged PR interval, cardiomyopathy, underlying structural heart disease, Wolff Parkinson-White syndrome);

**[For Cohort 1 only]** Screening supine 12-lead ECG demonstrating QTcF interval  $>450$  msec or a QRS interval  $>120$  msec;

**[For Cohort 2 only]** Screening supine 12-lead ECG demonstrating a QTcF interval  $>470$  msec or a QRS interval  $>120$  msec;

**NOTE:** If QTcF exceeds 450 msec (for Cohort 1) or 480 msec (for Cohort 2), **or** QRS exceeds 120 msec, the ECG should be repeated 2 more times and the average of the 3 QTcF or QRS values should be used to determine eligibility.

17. Participants with **ANY** of the following abnormalities in clinical laboratory tests at screening, as assessed by the study -specific laboratory and confirmed by a single repeat test, if deemed necessary:

- eGFR <60 mL/min/1.73m^2 based on the CKD-EPI equation, with single repeat allowed.
- **[For Cohort 1 only]**
  - AST **or** ALT level  $\geq$  ULN;
  - Albumin > ULN;
  - Prothrombin time > ULN;
  - Total bilirubin level  $\geq 1.5 \times$  ULN;

**NOTE:** Participants with a history of Gilbert syndrome (and hence elevated total bilirubin) are eligible provided direct bilirubin level is  $\leq$  ULN;

- **[For Cohort 2 only]** ALT **or** AST  $>5 \times$  ULN

18. In the opinion of the investigator or Pfizer (or designee), have any clinically significant laboratory abnormality that that could affect interpretation of study data or the participant's participation in the study.

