### 1.3. Schedule of Activities

The SoA table provides an overview of the protocol visits and procedures. Refer to the **STUDY ASSESSMENTS AND PROCEDURES** section of the protocol for detailed information on each procedure and assessment required for compliance with the protocol.

The investigator may schedule visits (unplanned visits) in addition to those listed in the SoA table, in order to conduct evaluations or assessments required to protect the well-being of the participant.

Visit Identifier a	Screening	Day -1	Day 1	Day 2	Day 3	Early Termination/ DC	Follow-up Contact
Days Relative to Day 1 Abbreviations used in this table can be found in Appendix 10	Day -28 to Day -2						28-35 Daysb
Informed consent	X						
Admission to CRU		X					
Confinement to CRU		X	→	→	X		
Inclusion/exclusion criteria	X	X					
Medical history	X	X					
Demography c	X						
Physical examination d	X	X			X	X	
Height and weight assessment	X						
Safety laboratory tests e	X	X			X	X	
Child-Pugh classification f	X						
History of illegal drug/tobacco/alcohol use	X	X					
Urine alcohol test or alcohol breath test	X	X					
Urine or serum pregnancy test (WOCBP only)	X	X			X	X	
Contraception check g	X	X			X	X	X
Serum FSH in post-menopausal females amenorrheic ≥12 months and under 60 years of age	X						
Urine drug screen	X	X					
Single supine 12-Lead ECG h	X		X		X	X	

PFIZER CONFIDENTIAL

Visit Identifier a	Screening	Day -1	Day 1	Day 2	Day 3	Early Termination/ DC	Follow-up Contact
Days Relative to Day 1 Abbreviations used in this table can be found in Appendix 10	Day -28 to Day -2						28-35 Daysb
Single, seated vital signs (BP, and pulse rate) i	X		X		X	X	
HIV, HBsAg, HBcAb, HCVAb testing j	X						
PF-07321332 administration			X				
Ritonavir administration k		X	X	X			
Plasma PK for PF-07321332 CCl [REDACTED] l			X	X	X	X	
CCl [REDACTED]			[REDACTED]	[REDACTED]			
Prior/concomitant treatments	X	X	→	→	X	X	X
COVID-19 testing o	X	X					
COVID-19 check temperature p	X	X	X	X	X		
COVID-19 questionnaire q	X	X					
CRU discharge					X		
Serious and nonserious adverse event monitoring	X	X	→	→	X	X	X
Standard meals		X	X r	X	X		

- a. Day relative to start of PF-07321332 dosing (Day 1).

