- b. Contact may occur via telephone contact and must occur 28 to 35 days from administration of PF-07321332 or from the time of early termination/discontinuation.
- c. Demographics will include race, age, and gender.
- d. Complete physical examination will be performed at screening; and limited PE will be conducted on Day -1, Day 3, early termination, and at any time point as deemed necessary by the investigator.
- e. Safety laboratory assessments include chemistry, hematology, and urinalysis (and microscopy, if needed) and must be collected following at least a 4 hour fast.
- f. The Child-Pugh classification ([Appendix 9](#)) will be used to define the participants of Cohort 2 with moderate hepatic impairment (Child-Pugh Class B) at Screening.
- g. Confirmation of the correct use of appropriate contraceptive method.
- h. Single 12-lead ECG readings will be taken pre-dose on Day 1 and at specified times. All ECG assessments will be made prior to any blood draws or vital sign measurements.
- i. Single seated BP and PR will be performed pre-dose on Day 1 and at specified times. All BP and PR will be measured prior to collection of blood draws if scheduled at the same time, after collection of ECGs.
- j. Testing will be performed as described in [Appendix 2](#).

PFIZER CONFIDENTIAL

Visit Identifier a	Screening	Day -1	Day 1	Day 2	Day 3	Early Termination/ DC	Follow-up Contact
Days Relative to Day 1 Abbreviations used in this table can be found in Appendix 10	Day -28 to Day -2						28-35 Daysb

k. Ritonavir will be administered on Day -1 at -12 hours, Day 1 at 0 hours and 12 hours, and Day 2 at 24 hours, relative to PF-07321332 dosing.  
l. Blood samples are to be collected for plasma PK assessment of PF-07321332 CCI [REDACTED] on Day 1 at 0 (pre-dose for PF-07321332), 0.5, 1, 2, 3, 4, 6, 8, 10, and 12 hours, Day 2 at 24 and 36 hours, and Day 3 at 48 hours, relative to PF-07321332 dosing, and at early termination/DC (if before 48 hours post-dose for PF-07321332), if needed.

CCI [REDACTED]  
[REDACTED]

o. Testing for COVID-19 pathogen will be performed prior to being admitted to the clinic for confinement, on Day -1, and if participant develops COVID-19 like symptoms.  
p. To be done at least daily during residence.  
q. Check exposure to positive case, residence or travel in area of high incidence and COVID-19 related signs and symptoms.  

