### **6. STUDY INTERVENTION(S) AND CONCOMITANT THERAPY**

Study intervention is defined as any investigational intervention(s), marketed product(s), placebo, medical device(s), or study procedure(s) intended to be administered to a study participant according to the study protocol.

For the purposes of this protocol, study intervention refers to PF-07321332 and ritonavir.

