#### **6.8.2. Participants with Impaired Liver Function (Cohort 2)**

Participants are permitted to be on stable doses (at least up to 5 half-lives) of background medications if they are considered necessary for the welfare of the study participants (eg, standard therapy for the underlying disease), are not contraindicated with the investigational product, and are unlikely to interfere with the PK of the investigational product. **Whenever possible**, attempts must be made to **not** alter the doses and regimens of the concomitant medications after Day 1 and until the end of study on Day 3.

- Approved concomitant medications should be administered to hepatically impaired participants at least 2 hours prior to dosing or withheld until 4 hours after PF-07321332 dosing.

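### For Cohort 2 participants in the intermediate blood-pressure band, the qualifying reading is set on Day 1, after the first ritonavir dose, and no Day -1 reading is scheduled

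*Protocol*

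**What the plan says.** Criterion 15 in Protocol Section 5.2 opens as a criterion on Screening vital signs. For Cohort 2 it has two stages.

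- **Stage one** excludes on the Screening reading: systolic 180 mm Hg or more and/or 100 mm Hg or more ("diastolic) following at least 5 minutes of rest"). A reading at or above the limit is repeated twice and the three values are averaged.
- **Stage two** covers SBP from 160 to below 180 mm Hg or DBP from 95 to below 100 mm Hg. For these participants "the period between Screening and Day -1 must be used to refine the doses of the agents used for management of BP"; the stated goal is stable pressure when Day -1 arrives. The bullet then ends: "Participants must have measurement on Day 1 of SBP" at or below 160 mm Hg, together with DBP below 95 mm Hg.

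On dosing, Section 6 says: "For the purposes of this protocol, study intervention refers to PF-07321332 and ritonavir". Footnote k of the Schedule of Activities (Section 1.3) gives the first dose: "Ritonavir will be administered on Day -1 at -12 hours". Section 6.1.1 agrees.

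On assessments, the Schedule row that begins "Single, seated vital signs (BP, and pulse rate" is marked at Screening, Day 1, Day 3 and early termination. It is blank at Day -1. Footnote i and Section 4.1 put the Day 1 reading before dosing on that day. The inclusion/exclusion row is marked at Screening and Day -1 only.

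**The concern.** An entry limit should be tested before a participant receives any study intervention. Here the stage-two limit is tied to a reading that follows the first ritonavir dose and the last scheduled eligibility review. The same bullet names Day -1 as the target for stable BP, yet the Schedule provides no reading that day to confirm it. The other repeat entry checks (urine drug screen, alcohol test, pregnancy test) are all scheduled on Day -1.

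Two things are at stake. The first is avoidable exposure: a participant who does not meet an entry limit may already have taken a dose. The second is an undefined case in a cohort of 8. The protocol does not say what happens to a participant who fails on Day 1. If dosing stops there, that person contributes nothing to the primary PK comparison.

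**Working it through.** This is mainly a check of sequence. Times are relative to the PF-07321332 dose.

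| Time | Event | Source (Protocol) |
|---|---|---|
| Day -28 to Day -2 | Screening BP; stage-one limit applied | Section 1.3; criterion 15 |
| Up to Day -1 | BP to be stabilised for the stage-two band | Criterion 15 |
| Day -1 | Last scheduled eligibility review; no BP scheduled | Section 1.3 |
| -12 h | First study-intervention dose (ritonavir) | Sections 1.3, 6 and 6.1.1 |
| Day 1, before 0 h | BP reading; stage-two limit applied | Criterion 15; Sections 1.3 and 4.1 |
| 0 h | PF-07321332 with ritonavir | Section 6.1.1 |

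A stage-two failure is therefore identified about 12 hours after one ritonavir dose and before any PF-07321332.

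**Disposition.** Section 7.1 lists adverse events, pregnancy and a positive COVID-19 test as reasons to stop study intervention. Section 7.2 lists refusal, loss to follow-up, death and termination by the sponsor. Neither list covers a failed Day 1 limit. Sections 5 and 8 rule out waivers. Replacement (Section 4.1) is discretionary and limited to non-safety reasons; whether a BP failure counts as one is not stated.

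**Size of one loss.** The visible text has no sample-size derivation to reproduce, so this is a side calculation. With equal variances, the log-scale 90% CI half-width is SD × t(0.95, n1+n2−2) × √(1/n1 + 1/n2).

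- 8 versus 8: 1.761 × √(1/8 + 1/8) = 1.761 × 0.500 = 0.881 × SD.
- 8 versus 7: 1.771 × √(1/8 + 1/7) = 1.771 × 0.518 = 0.917 × SD.
- Ratio: 0.917 / 0.881 = 1.041, about 4% wider.

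The SD is not given. For assumed log-scale SDs of 0.2 to 0.5, the upper confidence limit divided by the estimated ratio moves from 1.19–1.55 (8 versus 8) to 1.20–1.58 (8 versus 7).

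**The case against.** The strongest reply is that little can go wrong in practice. Section 8.2.2 permits extra BP readings as needed for safety data. Section 1.1 speaks of safety assessments on Day -1 before dosing. Adjusting BP treatment towards a Day -1 target presupposes that someone measures BP along the way. The Day 1 reading still precedes PF-07321332, and Section 8 sends safety issues to the sponsor for a decision on continuing. All of this is fair, and it means a failure need not first come to light on Day 1. But none of it schedules the check: permission is not a requirement, the Section 1.1 statement assigns no BP to Day -1, and both criterion 15 and Section 4.1 name Day 1.

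The objection also rightly limits several stronger readings that a reader might infer.

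- *All Cohort 2 BP eligibility is decided on Day 1.* It is not. The stage-one limit is applied at Screening, before any dosing, and the Day 1 limit most naturally covers only the stage-two band.
- *Criterion 15 conflicts with Section 6.8.2* ("Participants are permitted to be on stable doses (at least up to 5 half-lives) of background medications"). This is not shown. Dose refinement ends by Day -1, Screening can be as early as Day -28, and Section 6.8.2 asks that doses be left alone, where possible, after Day 1. Both can be met.
- *An SBP of exactly 160 mm Hg is classified two ways.* The value triggers refinement at one time and is acceptable on Day 1 at another. These are different readings with different consequences.
- *The Day 1 timing is what stops a failure being a screen failure.* Section 5.4 turns on enrolment, and Section 1.1 ties enrolment to taking part in study activity after screening. Someone failing on Day -1 could already count as enrolled.
- *Such a participant is certainly in the Safety Analysis Set.* The dosing condition is met, but the definition also requires random assignment, in a study that does not randomise.

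**Conclusion.** The point holds in a narrow form. For the stage-two band of Cohort 2, the plan sets the qualifying BP reading after the first dose of study intervention, schedules no reading at the last eligibility review, and gives no disposition for a failure. The exposure at issue is one ritonavir dose, not PF-07321332.

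The statistical effect is small. The 4% widening is the cost of one unreplaced loss, not an expected effect: the documents give no frequency of Day 1 failures, and replacement may be possible. It assumes equal variances, whereas SAP Section 8.1 and its Appendix 1 plan unequal variances with Kenward-Roger degrees of freedom. The true figure would therefore differ, and would be larger if Cohort 2 is the more variable group. The reasons to act are the avoidable exposure and the missing rule, rather than precision.

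**What to change.** Reconcile criterion 15, the Schedule of Activities (the vital-signs and eligibility rows, with footnotes i and k) and Section 4.1, so that this BP eligibility check falls at a visit where BP is scheduled and before the first dose of study intervention. State how a participant who fails the check is handled, including whether replacement applies and which analysis sets the participant enters. The BP limits, and any management of BP, are for the sponsor; none is proposed here.

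The cost is wording in the protocol and the Schedule, and at most one extra cuff reading in a participant who is already admitted to the unit.

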## 10.6. Appendix 6: Liver Safety: Suggested Actions and Follow-Up Assessments

### Potential Cases of Drug-Induced Liver Injury

Humans exposed to a drug who show no sign of liver injury (as determined by elevations in transaminases) are termed “tolerators,” while those who show transient liver injury but adapt are termed “adaptors.” In some participants, transaminase elevations are a harbinger of a more serious potential outcome. These participants fail to adapt and therefore are “susceptible” to progressive and serious liver injury, commonly referred to as DILI. Participants who experience a transaminase elevation above  $3 \times$  ULN should be monitored more frequently to determine if they are “adaptors” or are “susceptible.”

In the majority of DILI cases, elevations in AST and/or ALT precede TBili elevations ( $>2 \times$  ULN) by several days or weeks. The increase in TBili typically occurs while AST/ALT is/are still elevated above  $3 \times$  ULN (ie, AST/ALT and TBili values will be elevated within the same laboratory sample). In rare instances, by the time TBili elevations are detected, AST/ALT values might have decreased. This occurrence is still regarded as a potential DILI. Therefore, abnormal elevations in either AST OR ALT in addition to TBili that meet the criteria outlined below are considered potential DILI (assessed per Hy’s law criteria) cases and should always be considered important medical events, even before all other possible causes of liver injury have been excluded.

The threshold of laboratory abnormalities for a potential DILI case depends on the participant’s individual baseline values and underlying conditions. Participants who present with the following laboratory abnormalities should be evaluated further as potential DILI (Hy’s law) cases to definitively determine the etiology of the abnormal laboratory values:

- Participants with AST/ALT and TBili baseline values within the normal range who subsequently present with AST OR ALT values  $>3 \times$  ULN AND a TBili value  $>2 \times$  ULN with no evidence of hemolysis and an alkaline phosphatase value  $<2 \times$  ULN or not available.
- For participants with baseline AST **OR** ALT **OR** TBili values above the ULN, the following threshold values are used in the definition mentioned above, as needed, depending on which values are above the ULN at baseline:

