**Table 6. Derivation of Child-Pugh Classification Score**

Assessment Parameters	Assigned score for observed findings		
	1 point	2 points	3 points
Encephalopathy grade a (refer to Table 7 below)	0	1 or 2	3 or 4 a
Ascites	Absent	Asymptomatic	Requiring intervention
Serum total bilirubin, mg/dL	<2	2 to 3	>3
Serum albumin, g/dL	>3.5	2.8 to 3.5	<2.8
Prothrombin time, sec prolonged b	<4	4 to 6	>6

a. Participants with a prior history of Grade 3 or Grade 4 encephalopathy who are *currently* receiving an intervention [for example: lactulose or lactitol, alone or in combination with rifaximin, and/or neomycin] to manage encephalopathy-related signs and symptoms should be scored for encephalopathy grading *based on their presentation while on intervention at the Screening visit* and can be included in this study as long as they do *not* have clinically active Grade 3 or Grade 4 encephalopathy.

b. As assessed relative to PT control (*or* upper limit of normal).

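### Protocol 5.2: the Cohort 2 QTcF exclusion limit and its repeat trigger differ by 10 msec, and the Cohort 1 albumin limit excludes the side opposite to hepatic impairment

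*Protocol*

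**What the plan says.** Section 5.2 excludes a candidate if any one criterion applies, and Sections 5 and 8 rule out waivers. The wording of each limit therefore matters.

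**Criterion 16 (screening ECG).** For Cohort 2 the excluding finding is "Screening supine 12-lead ECG demonstrating a QTcF interval" above 470 msec. The Cohort 1 limit is 450 msec, and the QRS limit is 120 msec in both cohorts. The note below these limits reads "If QTcF exceeds 450 msec (for Cohort 1) or 480 msec (for Cohort 2"), or if QRS exceeds 120 msec, two further ECGs are taken and the mean of the three decides eligibility.

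**Criterion 15 (screening blood pressure).** When a reading reaches the cohort's limit, "the BP should be repeated 2 more times and the average of the 3 BP values should be used".

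**Criterion 17 (laboratory tests).** Five limits are tagged Cohort 1 only: AST or ALT at or above ULN, albumin above ULN, "Prothrombin time > ULN", and total bilirubin at or above 1.5 × ULN. An untagged eGFR limit (below 60) also applies to Cohort 1.

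**Judgement-based rules for controls.** Inclusion 3 requires a healthy participant on medical evaluation, laboratory tests included, and adds "No known or suspected hepatic impairment". Exclusion 18 removes those who, in the opinion of the investigator or sponsor, "have any clinically significant laboratory abnormality" that could affect the data or participation. Exclusion 6 also covers laboratory abnormalities.

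**The concern.** A repeat-and-average rule normally gives a reading over the limit a second look, so that one noisy measurement does not decide eligibility. That works only if the repeat is triggered at the exclusion limit. In Cohort 2 the QTcF trigger is above the limit, so a lower reading can be treated more strictly than a higher one.

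The albumin limit raises a different question. The other four limits tagged Cohort 1 only remove values that suggest liver disease. The albumin limit removes high values, whereas the protocol's own Child-Pugh table treats low albumin as the sign of dysfunction. As written, the only numeric albumin limit for controls does nothing to confirm that their liver function is normal.

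What is at stake is clear and consistent eligibility decisions in a study with 8 participants planned per cohort.

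**Working it through.** **1. QTcF and blood pressure: limit against repeat trigger.** All figures are from Section 5.2, criteria 15 and 16.

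| Measure | Exclusion limit | Repeat trigger | Equal? |
|---|---|---|---|
| Cohort 1 SBP, mm Hg | 140 | 140 | yes |
| Cohort 1 DBP, mm Hg | 90 | 90 | yes |
| Cohort 2 SBP, mm Hg | 180 | 180 | yes |
| Cohort 2 DBP, mm Hg | 100 | 100 | yes |
| Cohort 1 QTcF, msec | 450 | 450 | yes |
| Cohort 1 QRS, msec | 120 | 120 | yes |
| Cohort 2 QRS, msec | 120 | 120 | yes |
| Cohort 2 QTcF, msec | 470 | 480 | no |

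Seven of the eight match. The gap in the eighth is 480 − 470 = 10 msec.

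**2. What the rule does as written.** I take the average to be judged against the 470 msec limit, because the note gives no other. The readings below are illustrative.

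- First reading 475: above 470 but not above 480, so excluded with no repeat required by the note. Repeats of 465 and 465 would have given (475 + 465 + 465)/3 = 468.3, which is not above 470.
- First reading 485: above 480, so repeated. With repeats of 460 and 460 the mean is (485 + 460 + 460)/3 = 468.3, so not excluded.
- In general, a first reading of 485 qualifies when the two repeats average (3 × 470 − 485)/2 = 462.5 msec or less.

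**3. Can the mismatch change decisions?** The documents give no within-person SD, so I assume 5, 10 and 15 msec. Simulated independent normal readings around a true mean of 465 msec give these probabilities of exclusion:

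| Assumed SD, msec | As written (470/480) | Both 470 | Both 480 |
|---|---|---|---|
| 5 | 0.159 | 0.025 | 0.000 |
| 10 | 0.283 | 0.124 | 0.003 |
| 15 | 0.312 | 0.186 | 0.025 |

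These figures show only that the mismatch can alter eligibility for someone near the limit. They do not show which figure was intended.

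**4. Albumin: direction of each limit tagged Cohort 1 only.**

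- AST and ALT: high values excluded. Appendix 6 describes people who "show no sign of liver injury (as determined by elevations in transaminases"), so high is the impairment side.
- Total bilirubin and prothrombin time: high values excluded. Appendix 9 Table 6 gives more points as each rises.
- Albumin: high values excluded. In Table 6 the row "Serum albumin, g/dL" gives 1 point above 3.5, 2 points for 2.8 to 3.5 and 3 points below 2.8, so low is the impairment side.

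Four of the five exclude the impairment side; albumin does not, and it has no lower limit. Table 6 is used here for direction only, since Child-Pugh scoring does not apply to Cohort 1.

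**The case against.** **Low albumin in a control is already covered.** Largely true. Inclusion 3 and exclusions 6 and 18 can all remove such a person, and exclusion 4 and the other liver limits give further protection. The albumin limit also contradicts no other passage, and the documents do not state its purpose; that it was meant to support normal hepatic function is inferred from the limits listed with it. What stands is narrower: the numeric limit removes no low value, and the remaining safeguards against low albumin itself rest on judgement.

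**A candidate in the 470 to 480 msec band is not shut out.** Section 8.2.3 allows an abnormal ECG to be repeated to rule out poor lead placement, and Section 5.4 allows rescreening with sponsor approval. This stands, but neither route requires a repeat or supplies the averaging rule.

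**Section 8.2.3 might seem to settle the figure at 470 msec.** It does not. That passage is a post-dose monitoring trigger combined with a rise from baseline of at least 30 msec. Appendix 7 uses 480 msec for ECG findings of potential concern. Both figures serve other purposes, so neither decides the screening rule.

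**Criterion 1 might be read as barring Cohort 2.** It lists hepatic and neurological disease with no cohort tag. Inclusion 4, exclusions 4 and 5 and Section 4.1 make the intent plain, so this is an editorial matter and not a bar to enrolment.

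**Conclusion.** The point holds as a minor one. The QTcF mismatch is a definite numeric inconsistency: one of eight paired limits, with a band of 10 msec. The albumin limit is a probable drafting slip: one of the five limits tagged Cohort 1 only points away from impairment. The first conclusion rests on the text alone. The second also rests on the inference that the liver-related limits listed together share a purpose.

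A reader might infer that the control group will include people with impaired livers, or that the Test/Reference ratio is biased. The documents do not support that. They do not say how often low albumin would occur in otherwise eligible controls, and the judgement-based criteria remain in force. No bias in the ratio, no effect on its 90% confidence interval and no number of protocol deviations is claimed. The planned 8 per cohort and the ANOVA are unaffected.

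**What to change.** In one amendment to Section 5.2, the sponsor should:

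- reconcile the 470 and 480 msec figures in criterion 16, so that the Cohort 2 exclusion limit and its repeat trigger are the same number;
- reconcile the direction of the Cohort 1 albumin limit with the other liver limits in criterion 17;
- as an editorial remark only, state in criterion 1 that the qualifying hepatic disease of Cohort 2 is excepted.

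No threshold is proposed for any of these.

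The cost is mainly administrative. Under Section 10.1.1, changes to the study design need IRB/EC approval before implementation, and substantial amendments need health authority approval. Albumin is already in the chemistry panel (Appendix 2), and the Schedule of Activities already has safety laboratory tests at Screening, so no new laboratory test is needed. Depending on how the QTcF figures are reconciled, a Cohort 2 candidate with a first reading above 470 and up to 480 msec may need two further ECGs.
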